| STUDY OBJECTIVES | To evaluate the antitumor activity of GDC-0449 in terms of 6-month clinical benefit (Complete response, partial response and stable disease, as per the Response Evaluation Criteria in Solid Tumors, Revised RECIST criteria 2009). |
| Primary | |
| Secondary | 
 • Best overall response (as per the revised RECIST criteria 2009); • 1- and 2-year progression-free survival; • 1- and 2-year overall survival; • GDC-0449 safety; • Pharmacogenomic analysis of predictive markers of treatment outcome. |
| STUDY DESIGN | Single-arm phase 2 clinical trial based on two-stage Simon's design. |
| STUDY POPULATION | Adult patients with unresectable locally advanced or metastatic chondrosarcoma |
| INCLUSION CRITERIA | 
 1. Patients must have histologically confirmed diagnosis of chondrosarcoma (conventional, mesenchymal, dedifferentiated or clear cell subtypes) ; 2. Patients must have measurable disease (outside any previously irradiated field) defined as at least one lesion that can be accurately measured in at least one dimension (longest diameter to be recorded) as ≥ 10 mm with spiral CT scan. See Section 12 for the evaluation of measurable disease. 3. No more than three prior lines of chemotherapy for advanced disease (including no more than 450 mg/m² doxorubicin). At least three weeks since last chemotherapy (six weeks in case of nitrosoureas and mitomycin C), immunotherapy or any other pharmacological treatment and/or radiotherapy. 4. Age ≥ 18 years. 5. Life expectancy of greater than 3 months 6. ECOG performance status ≤ 2 (Karnofsky $\geq 60\%$; see Appendix A). 7. Patients must have normal organ and marrow function as defined below: 
 i. leukocytes $\geq 3,000/\text{mcL}$ ii. absolute neutrophil count $\geq 1,500/\text{mcL}$ iii. platelets $\geq 100,000/\text{mcL}$ iv. total bilirubin within normal institutional limits v. AST(SGOT)/ALT(SGPT) ≤ 2.5 X institutional upper limit of normal vi. Creatinine within normal institutional limits 
OR
 creatinine clearance ≥ 60 mL/min/1.73 m² for patients with creatinine levels above institutional normal |

| | |
|---------------------------|---|
| | 
8. Metastatic or unresectable locally advanced disease.
 
9. Documented disease progression (as per RECIST) before study entry.
 
10. Hh pathway inhibitors such as vismodegib have been demonstrated to be embryotoxic and/or teratogenic in multiple animal species and can cause severe midline defects, missing digits, and other irreversible malformations in the developing embryo or fetus. For this reason, women of child-bearing potential and men must use two forms of contraception (i.e., barrier contraception and one other method of contraception) at least 4 weeks prior to study entry, for the duration of study participation, and for at least 24 months post-treatment for female patients and for 2 months for male patients. For appropriate methods of contraception considered acceptable see Appendix C. Should a woman become pregnant or suspect she is pregnant while participating in this study, she should inform her treating physician immediately.
 
11. Pregnancy Testing. Women of childbearing potential are required to have a negative serum pregnancy test (with a sensitivity of at least 25 mIU/mL) within 7 prior to initiating GDC-0449 treatment (serum or urine). A pregnancy test (serum or urine) will be administered every 4 weeks while on study within the 24-hour period prior to the administration of GDC-0449. A positive urine test must be confirmed by a serum pregnancy test. Prior to dispensing GDC-0449, the investigator must confirm and document the patient's use of two contraceptive methods, dates of negative pregnancy test, and confirm the patient's understanding of the teratogenic potential of GDC-0449.
 
 i. Women of childbearing potential are defined as follows: ii. Patients with regular menses iii. Patients with amenorrhea, irregular cycles, or using a contraceptive method that precludes withdrawal bleeding iv. Women who have had a tubal ligation v. Women are considered not to be of childbearing potential for the following reasons: 
 vi. The patient has undergone hysterectomy and/or bilateral oophorectomy. vii. The patient is post-menopausal defined by amenorrhea for at least 1 year in a woman > 50 years old. viii. The patient has permanent premature ovarian failure confirmed by specialist gynecologist 
12. Ability to understand and the willingness to sign a written informed consent document.
 
13. In accordance with French Regulatory Authorities: Patients with French Social Security in compliance with the French law relating to biomedical research (Huriet Law 88-1138 and related decrees).
 |
| EXCLUSION CRITERIA | 
 1. Tumor tissue sample not available for pathological review and/or correlative studies. 2. Patients who have had chemotherapy or radiotherapy within 3 weeks (6 weeks for nitrosoureas or mitomycin C) prior to entering the study or those who have not recovered from adverse events due to agents administered more than 3 weeks earlier. 3. Patients may not be receiving any other investigational agents. 4. Patients with known brain metastases should be excluded from this clinical trial because of their poor prognosis and because they often develop progressive neurologic dysfunction that would confound the evaluation of neurologic and other adverse events. 5. History of allergic reactions attributed to compounds of similar chemical or biologic |

| | |
|--|---|
| | 
composition to GDC-0449 or other agents used in the study.
 
 6. Patients with malabsorption syndrome or other condition that would interfere with intestinal absorption. Patients must be able to swallow capsules. 7. Patients with clinically important history of liver disease, including viral or other hepatitis or cirrhosis are ineligible. 8. Patients with uncontrolled hypocalcemia, hypomagnesemia, hyponatremia or hypokalemia defined as less than the lower limit of normal for the institution, despite adequate electrolyte supplementation are excluded from this study. 9. Uncontrolled intercurrent illness including, but not limited to, ongoing or active infection, symptomatic congestive heart failure, unstable angina pectoris, cardiac arrhythmia, or psychiatric illness/social situations that would limit compliance with study requirements. 10. Pregnant women are excluded from this study because GDC-0449 is a Hh pathway inhibiting agent with the potential for teratogenic or abortifacient effects. Because there is an unknown but potential risk for adverse events in nursing infants secondary to treatment of the mother with GDC-0449, breastfeeding should be discontinued if the mother is treated with GDC-0449. 11. HIV-positive patients on combination antiretroviral therapy are ineligible because of the potential for pharmacokinetic interactions with GDC-0449. In addition, these patients are at increased risk of lethal infections when treated with marrow-suppressive therapy. Appropriate studies will be undertaken in patients receiving combination antiretroviral therapy when indicated. |
| STUDY POPULATION Translational research study | All patients included in the trial are eligible for the translational research study. |
| NUMBER OF PATIENTS | Based on the following hypotheses under GDC-0449 treatment: 20% clinical benefit (null hypothesis), 40% acceptable clinical benefit (alternative hypothesis), 10% type I error rate, 90% power, a total of 37 assessable patients will be necessary (17 for the first stage + 20 for the second stage). In order to account for not assessable patients (+/- 20%), 45 patients will be recruited. |
| NUMBER OF SITES | This is a multicenter study. A complete list of investigators will be provided as a separate document. |
| STUDY DRUG FORMULATION | GDC-0449 – Capsules packaged in 75 mL bottles. Each bottle contains 32 capsules. |
| ROUTE OF ADMINISTRATION | GDC-0449: Oral |
| ADMINISTERED DOSE | GDC-0449: 150 mg, take with or without food at the same time every day |
| TREATMENT SCHEDULE | GDC-0449: Days 1-28 |

| | |
|---------------------------------------|--|
| EFFICACY EVALUATIONS | 
Patients will be evaluated for efficacy if they receive at least one complete or two incomplete cycles of GDC-0449, and if they have at least one disease measurement recorded not less than eight weeks after treatment onset (except for in case of early disease progression).
 
Antitumor activity will be assessed using RECIST on a set of measurable lesions identified at baseline as target lesions and followed until disease progression by the appropriate method (computed tomography [CT] scan or magnetic resonance imaging [MRI]).
 
Radiological and clinical (whenever appropriate) tumor assessment will be performed at baseline and every eight weeks until evidence of disease progression (PD). Whenever the criteria of response are met, the appropriate imaging tests will be repeated at least four weeks later in order to confirm the response. Beyond 48 months of treatment without evidence of progressive disease, radiological tumor assessment will be performed every 3 months.
 
Efficacy will be evaluated based on 6-month clinical benefit rate (primary objective), best overall response, 1- and 2-year PFS, and 1- and 2-year OS.
 |
| SAFETY EVALUATIONS | 
Patients will be evaluable for safety if they have received at least one dose of GDC-0449. All AEs will be graded according to the CTEP CTCAE Version 4.0. Safety profile will be continuously followed during treatment and up to 30 days after the last GDC-0449 dose or until the start of a new antitumor therapy, whichever occurs first.
 |
| TRANSLATIONAL RESEARCH PROGRAM | 
The following analyses will be done on tumor samples from patients treated with GDC-0449:
 
 - Analysis of the mutational status of PTCH and SMO - Analysis of the expression pattern of hedgehog signaling molecules (Shh, PTCH, SMO, GLI-1, GLI-2, GLI-3) by using quantitative reverse transcription-polymerase chain reaction and immunohistochemistry (IHC). 
The 6-months clinical benefit rate will be correlated with the mutational status of PTCH and SMO and with the expression score of hedgehog signaling molecules in order to identify predictive factors of clinical benefit from GDC-0449.
 |

TABLE OF CONTENTS

| | |
|---|----|
| SUMMARY OF CHANGES | I |
| SYNOPSIS | 3 |
| TABLE OF CONTENTS | 7 |
| 1. OBJECTIVES | 11 |
| 1.1. Primary Objective | 11 |
| 1.2. Secondary Objectives..... | 11 |
| 1.3. Study design and calendar..... | 11 |
| 2. BACKGROUND | 11 |
| 2.1 Study Disease..... | 11 |
| 2.2 GDC-0449..... | 12 |
| 2.3 Rationale | 21 |
| 2.4 Correlative Studies Background | 21 |
| 3. PATIENT SELECTION | 22 |
| 3.1 Eligibility Criteria | 22 |
| 3.2 Exclusion Criteria | 23 |
| 3.3 Inclusion of Women and Minorities | 24 |
| 4. REGISTRATION PROCEDURES..... | 24 |
| 4.1. General Guidelines..... | 24 |
| 4.2. Registration Process..... | 25 |
| 5. TREATMENT PLAN..... | 26 |
| 5.1 Agent Administration | 26 |
| 5.1.1 GDC-0449..... | 26 |
| 5.2 General Concomitant Medication and Supportive Care Guidelines..... | 26 |
| 5.2.1 GDC-0449..... | 26 |
| 5.3 Duration of Therapy..... | 28 |
| 5.4 Duration of Follow Up..... | 28 |
| 5.5 Criteria for removal from Study..... | 28 |
| 6. DOSING DELAYS/DOSE MODIFICATIONS | 28 |
| 7. ADVERSE EVENTS: LIST AND REPORTING REQUIREMENTS..... | 29 |
| 7.1 Comprehensive Adverse Events and Potential Risks Lists (CAEPRs) for GDC-0449 | 29 |
| 7.2 Adverse Event Characteristics [Following NCI procedures] | 33 |
| 7.3. Expedited Adverse Event Reporting [Following NCI procedures] | 33 |

| | | |
|--------------|---|----|

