11.1.6 Progression-Free Survival (PFS)

PFS is defined as the duration of time from start of treatment to time of progression or death, whichever occurs first.

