11.1.7 Overall Survival (OS)

OS is defined as the duration of time from start of treatment to the time of death

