13.2 Sample Size/Accrual Rate

The data from the literature about survival of patients with advanced chondrosarcomas are almost non-existent. However, some studies confirm that the prognosis of patients with metastatic chondrosarcomas is poor and similar to that observed in metastatic soft-tissue tumors with median survival ranging from 7 to 17 months ([Dickey et al., 2004](#); [Ries et al., 2007](#); [Giuffrida et al., 2009](#)). Therefore, we believe that a 6 months clinical benefit rate of 40% is a reasonable objective in this setting. This objective was also chosen by American investigators (SARC) in a phase 2 trial of perifosine in patients with chemo-insensitive sarcomas (including chondrosarcomas).

We rely on an optimal two-stage Simon's design (Simon, 1989). Based on the following hypotheses under GDC-0449 treatment:

- 20% non-progression rate (null hypothesis),
- 40% acceptable non-progression rate (alternative hypothesis),
- 10% type I error rate,
- 90% power,

a total of 37 assessable subjects will be necessary, with 17 assessable subjects recruited to the first stage.

Stage 1: Following the inclusion of the first 17 assessable patients, if 3 or less patients are progression-free (complete response, partial response or stable disease), the study would be terminated early. Otherwise, the second group of 20 subjects will be recruited.

Stage 2: If at the end of recruitment, 11 patients or more are progression-free (out of the 37 evaluable patients), GDC-0449 would be considered worthy of further testing in this disease.

To be evaluable, a subject must meet the eligibility criteria AND have received at least one complete or two incomplete cycles of GDC-0449 AND at least one disease measurement recorded not less than eight weeks after treatment onset.

Given the disease is rare and the absence of standard treatment in this indication, inclusion will not be suspended after the recruitment of the first 17 patients. Inclusion will be pursued, while data on the first 17 patients will be analyzed.

In order to account for not evaluable patients (+/- 20%), **45 patients will be recruited.**

The anticipated accrual rate is 2-3 patients/months.

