13.4 Analysis of Secondary Endpoints

Proportions (will be calculated and reported with their 95% confidence interval (binomial law).

Progression-free and overall survivals will be analyzed using the Kaplan-Meier method. The median survival rates will be reported with a 95% confidence interval. Median follow-up will be calculated using the reverse Kaplan-Meier method.

Duration of response will be described in responding subjects using descriptive statistics (median, extreme values, etc.).

The predictive value of biomarkers will be investigated using multivariate logistic regression (when evaluating impact on tumour response) or a Cox Proportional hazard model (when evaluating impact on time to tumour response) after checking for the proportional hazards assumption.

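### As written, the synopsis applies the efficacy-evaluable filter to 1- and 2-year PFS and OS, both timed from start of treatment, and section 13.4 names no other population, so some early deaths could be left out

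*Combined protocol and SAP*

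**What the plan says.** The Efficacy Evaluations row of the synopsis sets the entry rule: "Patients will be evaluated for efficacy if they receive at least one complete or two incomplete cycles of GDC-0449", together with "at least one disease measurement recorded not less than eight weeks after treatment onset (except for in case of early disease progression". The last sentence of that row lists what efficacy covers: "Efficacy will be evaluated based on 6-month clinical benefit rate (primary objective), best overall response, 1- and 2-year PFS, and 1- and 2-year OS".

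The time origins are in sections 11.1.6 and 11.1.7: "PFS is defined as the duration of time from start of treatment to time of progression or death, whichever occurs first", and "OS is defined as the duration of time from start of treatment to the time of death". Neither definition mentions an analysis set.

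Section 13.4 gives only the method: "Progression-free and overall survivals will be analyzed using the Kaplan-Meier method". It states no population and no landmark.

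Other sections also use evaluability conditions, but not for survival:
- Section 11.1.1 ties the cycle condition to objective response.
- Section 13.2 ties the cycle condition, and "at least one disease measurement recorded not less than eight weeks after treatment onset", to the Simon count, there without the exception for early progression.
- Section 13.5.2 ties eligibility and the cycle condition to the main response-rate analysis. Its rule that every included patient is assessed also concerns response.

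The Safety Evaluations row of the synopsis defines a set of all patients with at least one dose. No section assigns PFS or OS to it.

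**The concern.** The only efficacy population stated for PFS and OS depends on what happens after treatment starts: receiving enough treatment and reaching a measurement at week 8 or later. The survival clock nevertheless starts at first dose. A patient who dies in week 5 with no recorded progression contributes an OS event and a PFS event under sections 11.1.6 and 11.1.7, yet fails the synopsis rule and is never counted. Those who remain have, by construction, either reached the week-8 measurement or progressed early. This is immortal-time selection, and it pushes the curve up.

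The exception for early progression helps but does not close the gap:
- The first scheduled tumour assessment after baseline is at week 8, so an earlier progression is recorded only if something prompts an assessment.
- Section 11.1.4 says that symptomatic deterioration does not describe an objective response.
- Section 13.5.2 codes early death (from disease, toxicity or other cause) separately from progressive disease.
- The exception is attached to the scan condition. Whether it also waives the cycle condition is unclear.

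Four secondary endpoints are at stake: PFS and OS, each at 1 and 2 years. Kaplan-Meier handles short follow-up by censoring and needs no such filter.

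**Working it through.** **Plan's own figure.** The documents give no expected 1- or 2-year PFS or OS, so there is no survival figure to reproduce. The figures they do give are for the Simon design (17 then 37 patients; stop at 3 or fewer; success at 11 or more). It reproduces with type I error 0.0948 and power 0.9033, and uses neither PFS nor OS estimates.

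**Inputs**
- Median survival 7 to 17 months (section 13.2).
- 45 patients recruited (section 13.2).
- Scan condition at 8 weeks (synopsis): 56 / 30.4375 = 1.84 months.
- 6-month non-progression rates of 20% and 40% (section 13.2), used for PFS.
- Assumption: exponential survival. The documents give no shape.
- Assumption: the share f of deaths before week 8 that the filter removes. The documents give no value, so a range is shown.

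**Formulas**
- Deaths before week 8: d = 1 − 0.5^(1.84/m), with m the median in months.
- OS in all treated patients: S(t) = 0.5^(t/m).
- OS after the filter: S(t) / (1 − f·d).

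**Deaths before week 8**
- m = 7: d = 1 − 0.5^(1.84/7) = 16.7%, or 7.5 of 45.
- m = 17: d = 1 − 0.5^(1.84/17) = 7.2%, or 3.3 of 45.

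**1-year OS**

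| Early deaths removed (f) | m = 7 | m = 17 |
|---|---|---|
| none (all treated) | 30.5% | 61.3% |
| 25% (exception keeps three quarters) | 31.8% | 62.4% |
| 50% | 33.2% | 63.6% |
| 100% (exception keeps none) | 36.6% | 66.1% |

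The overstatement is 31.8 − 30.5 = 1.3 and 62.4 − 61.3 = 1.1 points at f = 25%. At f = 100% it is 36.6 − 30.5 = 6.1 and 66.1 − 61.3 = 4.8 points.

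**2-year OS.** At f = 100%, from 9.3% to 11.1% (m = 7) and from 37.6% to 40.5% (m = 17), so at most 1.8 to 2.9 points.

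**1-year PFS.** With an exponential through the 6-month rates, 1-year PFS is 0.20² = 4.0% or 0.40² = 16.0%. Removing every event before week 8 would give 6.6% or 21.2%. Most of those events are presumably progressions, which are exempt from the scan condition. If only 10 to 25% of early events are removed, the figures are 4.2 to 4.4%, or 16.4 to 17.0%.

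**Sampling error for scale.** The standard error of 1-year OS with 45 patients and no censoring is √(0.305 × 0.695 / 45) = 6.9 points, or √(0.613 × 0.387 / 45) = 7.3 points.

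The calculation covers early deaths only. It does not model patients who miss the cycle condition while still alive.

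**The case against.** The strongest reply is that the restriction comes from reading two sentences of one synopsis cell together. The body of the protocol attaches evaluability to response and to the Simon count, never to survival. Sections 11.1.6 and 11.1.7 carry no such condition, section 5.4 follows patients until death or study discontinuation, and a week-8 measurement has no function for OS. A sensible analyst might use all treated patients anyway. This stands in part: the body does not impose the filter on PFS or OS. But it does not name another set either, which leaves the synopsis rule as the only one stated.

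The size can also be challenged, and fairly:
- Entry requires a life expectancy above 3 months, so deaths before week 8 should be fewer than a constant hazard implies.
- The exception does not say that progression must be documented, and the synopsis allows clinical tumour assessment. Some early disease deaths may therefore be kept.
- The shift is below one standard error at this sample size. Unlike sampling error, however, it is systematic and avoidable.

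A reader might also infer more than the documents support. They do not show that all early deaths drop out, because early progression is excepted. They do not require several completed cycles, because one full or two partial cycles suffice. Nor can it be said that the results will look too good against published survival: the documents do not describe how the cited series selected patients, and sections 13.1 to 13.5 plan no such comparison for PFS or OS.

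**Conclusion.** The point holds in a limited form. The synopsis, as written, puts PFS and OS in a set defined by post-baseline events, and nothing in section 13 replaces it. Following that text biases OS upward, and PFS probably less.

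Under exponential survival with medians of 7 to 17 months, 1-year OS is overstated by about 1 point if the exception keeps three quarters of early deaths, and by at most 4.8 to 6.1 points if it keeps none. Both ends are upper-range because of the life-expectancy criterion.

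It would go too far to say that the trial's survival is overstated. That depends on whether the analyst applies the synopsis rule to survival and on how the exception is read, and the documents settle neither. The go/no-go decision is not affected, because it rests on the 6-month count alone. The change should still be made, since it decides which patients enter the survival curves.

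**What to change.** State in the synopsis and in section 13.4 that PFS and OS are analysed by Kaplan-Meier, from start of treatment, in all patients who received at least one dose, which is the set already defined for safety. Limit the evaluable set to the response-type endpoints: 6-month clinical benefit and best overall response.

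The cost is one sentence, entered in both places. No extra data are needed. The survival figures may come out slightly less favourable than under the synopsis rule.

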1. OBJECTIVES

1.1. Primary Objective

To evaluate the antitumor activity of GDC-0449 in terms of 6-month clinical benefit rate (Complete response, partial response and stable disease, as per the Response Evaluation Criteria in Solid Tumors, revised RECIST criteria 2009).

1.2. Secondary Objectives

- Best overall response (as per the revised RECIST criteria 2009);
- 1- and 2-year progression-free survival;
- 1- and 2-year overall survival;
- GDC-0449 safety;
- Pharmacogenomic analysis of predictive markers of treatment outcome.

